7.2.5 Patch Testing

In the event that a subject has an LSR that is felt to be suggestive of allergic contact dermatitis, patch testing may be initiated to confirm. This should be offered to the subject/caregiver. If the subject/caregiver consents to patch testing and once the LSR has been completely resolved for a period of 2 weeks and up to 2 months, patch testing will commence. Novan will provide the patch testing instruction once requested from the CRO medical monitor. Additional drug product for

patch testing may be supplied through IWRS if the currently assigned subject's investigational product has been assignment was > than 60 days of the patch testing date(s).

If allergic contact dermatitis is suspected, study drug should be discontinued permanently and an AE of allergic contact dermatitis should be recorded as the reason for discontinuation. Week 12/ET1 assessments should be completed at the time of discontinuation, but the subject should continue to participate in the study and complete study related visits through Week 24.

In the event of suspected allergic contact dermatitis, photographs may be taken of the affected area(s) and transmitted to the CRO medical monitor for review prior to initiating patch testing.

See [Section 20.2](#) for further information.

7.2.6 Scarring/Keloid Assessment

Scar formation will be assessed starting at the Week 4 visit through Week 12, and again at Week 24. For the purposes of this study, scar is defined as follows: pitted scars with ≥ 5 mm in diameter or ≥ 1 mm in depth, and hypertrophic/keloid scars originated from MC lesion. Pitted scars < 5 mm in diameter and < 1 mm in depth originated from MC lesion are considered part of normal healing process and will not be captured as AEs.

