3.3 Exploratory Endpoints

- Proportion of subjects who have a recurrence of MC after the first visit at which complete clearance was observed
- Proportion of subjects developing scar(s) after clearance of lesion(s) at each visit (Weeks 4, 8, 12, 24)
- Proportion of subjects with complete clearance of all treatable MC at each visit (Weeks 2, 4)

- Proportion of subjects achieving at least a 75% reduction from Baseline in the number of all treatable MC at each visit (Weeks 2, 4, 8, 12)
- Change from baseline of the composite score from age-matched (at baseline) Dermatology Life Quality Index (DLQI) assessment at Week 12 at Week 12
- Subject-reported spread to household members as measured by any new occurrence of MC in household members of subjects at each visit (Weeks 2, 4, 8, 12)
- Mean change from Baseline in number of treatable MC at each visit (Weeks 2, 4, 8, 12)
- Mean percent change from Baseline in number treatable MC at each visit (Weeks 2, 4, 8, 12)
- Time to complete clearance of all treatable MC

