Clinically significant LSRs reported as AEs and/or subject reported intolerance (i.e. itching, pain) may result in an investigator-directed temporary treatment hold (drug holiday), and topical corticosteroids may be used to treat LSRs for up to 2 weeks. If a drug holiday is prescribed, Investigational product (IP) will still be dispensed at the clinic visit to ensure the subject may resume dosing prior to the next clinic visit. The subject may reinitiate study drug treatment prior to the next scheduled visit. Upon re-initiation of study drug treatment, if a subject develops worsening LSRs, allergic contact dermatitis may be suspected. The investigator may take photographs of the suspected allergic contact dermatitis and discuss possible confirmation of allergic contact dermatitis with the CRO medical monitor. The investigator should also discuss necessity of patch testing with the subject/caregiver. The investigator will then discontinue the subject from study drug treatment and treat the area(s) with corticosteroids for up to 2 weeks. If the subject provides consent/assent, the investigator will consult the clinical research organization (CRO) medical monitor to implement the process for patch testing.

Adverse events will be assessed and collected after the initiation of study drug treatment through the end of the subject's last visit. Treatment-related adverse events will be followed up until resolution or up to one year after last treatment, whichever occurs earlier.

Scar formation will be assessed starting at the Week 4 visit through Week 12 and again at Week 24. The investigator will map locations of the molluscum lesions at Baseline. Additional lesions identified through Week 12 will be added to the map. Using the map as a guidance, the investigator will assess the treated areas for scar/keloid formation. MC lesions may resolve with pitted scars (indentation), and the small scars that maintain original MC size (<5 mm) and less than 1 mm in depth will heal over time. Any pitted scars <5 mm in diameter and <1 mm in depth will not be considered AEs since these are considered part of the normal healing process. . If a scar is larger than 5 mm in diameter or greater than 1 mm in depth, this will be considered an adverse event for the purposes of this study. In addition, keloid/hypertrophic scars will also be recorded as adverse events.

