If a subject's treatment is discontinued by the investigator or the subject because of an AE, that AE should be indicated as the reason for treatment discontinuation. All subjects will be encouraged to remain in the study throughout the 24-week study duration.

In the event of suspected allergic contact dermatitis, photographs may be taken of the affected area(s) and transmitted to the CRO medical monitor for review prior to initiating patch testing.

When approximately 200 subjects (cumulative across studies NI-MC302 and NI-MC302) have completed 4 weeks of treatment, a Data Safety Monitoring Board (DSMB) will review all available unblinded safety data (including completed patch testing results).

Table 1: Schedule of Assessments

	Screening	Treatment					
	Screening ¹ (Day -14 to Day 1)	Visit 1 ¹ Baseline (Day 1)	V2 Telephone Contact (Day 2)	Visit 3 ² Week 2 (Day 15 ±3)	Visit 4 ² Week 4 (Day 29 ±5)	Visit 5 ² Week 8 (Day 57 ±5)	Visit 6 ² Week 12/ ET1 (Day 85 ±5)
Informed Consent (Assent)	X						
Demographics	X						
Medical and Medication History	X						
Lesion Count or Recurrence	X	X		X	X	X	X
Physical Exam		X					X
Urine Pregnancy Test ³	X	X			X	X	X
BOTE Inflammation Score ⁴		X (pre-dose)		X	X	X	X
Local Skin Reactions (LSR) (post-dose) ⁴		X		X	X	X	X
Scarring/Keloid Assessment					X	X	X
DLQI/CDLQI ⁵		X					X
Review of Inclusion/Exclusion Criteria	X	X					
Drug Dispensed		X			X	X	
Dispense Subject Diary		X		X	X	X	
Review Subject Application Instructions		X		X	X	X	
In Clinic Study Drug Application ⁶		X		X	X	X	X
Review Study Drug Compliance				X	X	X	X
Collect Study Drug					X	X	X
Collect Subject Diary				X	X	X	X
Record Adverse Event (AE) and Concomitant Medication (CM) Changes ⁷		X	X	X	X	X	X

	Safety Follow-up		
	Visit 7 ² Week 16 Telephone Contact (Day 113±5)	Visit 8 ² Week 20 Telephone Contact (Day 141±5)	Visit 9 ² Week 24/ ET2 (Day 169±5)
Scarring/Keloid Assessment			X
Record Adverse Event (AE) and Concomitant Medication (CM) Changes ⁷	X	X	X

¹Screening and Baseline may occur on the same day. If this occurs, lesion count and review of inclusion/exclusion criteria will only occur once. If two members of the same household qualify for study participation, they must be randomized on the same day.

²All visit dates are in reference to Baseline, e.g. Week 2 occurs 14 days after Baseline Visit.

³Females 9 years of age and older.

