5.3 Exclusion Criteria

1. Have strongly suggested sexually transmitted MC and do not agree to refrain from sexual activities throughout the study period.
2. Are immunosuppressed, have immunodeficiency disorder, or are on immunosuppressive treatment;
3. Have significant injury on and/or surrounding MC that may impact ability to treat and count lesions;
4. Have received treatment with topical calcineurin inhibitors or steroids on MC or within 2 cm of MC lesions within 14 days prior to Baseline;
5. Have received treatment for MC during the 14 days prior to Baseline with podophyllotoxin, imiquimod, cantharidin, sinecatechins, topical retinoids, oral or topical zinc, or other homeopathic or over the counter (OTC) products including, but

- not limited to, ZymaDerm and tea tree oil, cimetidine and other histamine H2 receptor antagonists (including Zantac);
6. Have received surgical procedures related to MC (cryotherapy, curettage, other) within 14 days prior to Baseline;
 7. Have MC only in periocular area;
 8. Female subjects who are pregnant, planning a pregnancy or breastfeeding;
 9. Have known hypersensitivity to any ingredients of SB206 or Vehicle Gel including excipients;
 10. Have participated in a previous study with a berdazimer sodium product (SB204, SB206, SB208, SB414);
 11. Have more than 1 family member currently participating in a study with a berdazimer sodium product (SB204, SB206, SB208, SB414)
 12. Have participated in any other trial of an interventional investigational drug or device within 14 days or concurrent participation in another interventional research study.
 13. History or presence of clinically significant medical, psychiatric, or emotional condition that, in opinion of the investigator, would compromise the safety of the subject or the quality of the data.

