7.1 Efficacy Assessments

7.1.1 *Molluscum Contagiosum Lesion Counts*

Molluscum contagiosum is a viral infection characterized by small, discrete, waxy, skin-colored, dome-shaped papules, an average of 3–5 mm in diameter. The papules may be umbilicated and contain a caseous plug. When the lesions are squeezed or traumatized, a creamy, grey-white material can be extruded. If the investigator cannot clearly differentiate the lesions as is the case for agminated (clustered lesions) this should be counted as one lesion. If the investigator can differentiate and count the umbilical tops separately, each lesion should be counted separately. The

investigator should be consistent with the method of recording agminated lesions throughout the study.

For the purpose of this clinical trial, only active MC lesions are counted. Treatable lesions are any active (raised, palpable) MC lesions that are dome-shaped, pearly and shiny white top centered papules that are at least 2 cm away from the ocular region.

All study personnel who will perform lesion counts must pass the study training including lesion count training. Training on how to accurately count the number of MC lesions will be provided.

Mapping of lesions: At every visit from Baseline through Week 12, all lesions should be recorded on the body map and will clearly note the location of each lesion or agminated lesion. The lesion map is intended to assist study personnel in performing lesion counting and scar/keloid assessment.

Definition of Clearance: For the purpose of this study, “clear” means resolution of the active (raised, palpable) treatable molluscum lesion(s). After resolution, the residual surface changes such as pitted scar (indentation) < 1 mm in depth at the molluscum lesion area (<5 mm in diameter), hyper or hypopigmentation may remain. As these are considered part of the normal healing, they will not be captured as adverse events. Refer to the lesion count training for details.

The same evaluator should perform lesion counts at Screening, Baseline, and Weeks 2, 4, 8 and 12/ET1. In the event that this is not possible due to unforeseen circumstances, a different evaluator may evaluate the subject. The evaluator must pass the study training including lesion count training. It is particularly important to ensure the same evaluator performs the Baseline and Week 12/ET1 for lesion count for a subject and also Baseline and Week 24/ET2 assessment for scarring/keloid scarring.

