2	Pink or light red	Moderate	Crusting < 50%	Mild, palpable	Scant transudate or exudate	Moderate erosion
3	Red, restricted to treatment area	Coarse	Crusting > 50%	Moderate	Moderate transudate or exudate	Marked, extensive
4	Red extending outside treatment area	Scaling extending outside treatment area	Crusting extending outside treatment area	Marked swelling extending outside treatment area	Marked transudate or exudate	Black eschar or ulceration

Clinically significant LSRs that are reported as AEs and/or subject-reported intolerance (i.e., itching, pain) may result in an investigator-directed temporary treatment hold (drug holiday), and topical corticosteroids may be used to treat LSRs for up to 2 weeks. The subject may re-initiate study drug treatment prior to the next scheduled visit. Upon re-initiation of study drug treatment, if a subject develops worsening LSRs, allergic contact dermatitis may be suspected. The investigator may take photographs of the suspected allergic contact dermatitis and discuss possible confirmation of allergic contact dermatitis with the contract research organization's

(CRO) medical monitor. The investigator should also discuss the necessity of patch testing with the subject/caregiver. The investigator will then discontinue the subject from study drug treatment and treat the area(s) with corticosteroids for up to 2 weeks. If the subject provides consent/assent, the investigator will consult with the CRO's medical monitor to implement the process for patch testing.

Adverse events will be assessed and collected after the initiation of study drug treatment through the end of the subject's last visit. Treatment-related AEs will be followed up until resolution or up to 1 year after last treatment, whichever is sooner.

Scar formation will be assessed starting at the Week 4 visit through Week 12 and again at Week 24. The investigator will map locations of the molluscum lesions at Baseline. Additional lesions identified through Week 12 will be added to the map. Using the map as a guidance, the investigator will assess the treated areas for scar/keloid formation. The investigator will count and record the number of active (raised, treatable) molluscum lesions per body area. If a new scar is noted after the subject treated with study drug, this will be considered an AE for the purposes of this study. In addition, keloid/hypertrophic scars will also be recorded as AEs.

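### Protocol 7.1.1 assumes a Baseline scar assessment that is never scheduled, and SAP 10.1 counts scar presence, so old scars near treated lesions may not be reliably separated from new ones

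*Combined protocol and SAP*

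**What the plan says.** Protocol 7.2.6 sets the timing of scar assessment: "Scar formation will be assessed starting at the Week 4 visit through Week 12, and again at Week 24". The "Scarring/Keloid Assessment" row of Table 1 (under 4.1) matches, with marks at Weeks 4, 8, 12 and 24 only. The 13-step Baseline list in 6.2.2 includes lesion mapping and a brief physical examination but no scar item. The first visit list with one is Week 4 (6.2.5).

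Protocol 7.1.1 reads differently. It calls it particularly important that the same evaluator does the Baseline and Week 12 lesion counts "and also Baseline and Week 24/ET2 assessment for scarring/keloid scarring".

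The protocol endpoint in 3.3 concerns development: "Proportion of subjects developing scar(s) after clearance of lesion(s) at each visit (Weeks 4, 8, 12, 24". Section 10.1 of the final SAP derives it from a Yes to either of two eCRF questions. One asks about a scar above a stated depth or width. The other asks only whether a scar was present. Keloid or hypertrophic scarring has its own yes/no presence question. None refers to Baseline. SAP section 4 nevertheless ties the adverse event to newness: "If a new scar is noted after the subject treated with study drug, this will be considered an AE".

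**The concern.** The protocol's own account makes scars at entry foreseeable. Section 1.2 puts a single lesion at about 2 months but the infection at often more than a year, and 1.1 cites a mean time to resolution of 13.3 months. Many subjects will therefore already have had lesions come and go. Section 4.1 accepts that lesions can heal with pitted scars. Earlier ablation is barred only for a short period; the exclusion reads "Have received surgical procedures related to MC (cryotherapy, curettage, other) within 14 days prior to Baseline".

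Without a Baseline record, an old scar inside a treated area can be noted at Week 4 or later and enter the endpoint as if it had developed on study. Freedom from scarring is part of the rationale for the product (synopsis and 1.2), and qualifying scars are adverse events. If judged treatment-related, they are followed for up to a year (9.4.1). Keloid, hypertrophic or unresolved scars also call for a narrative (SAP section 6).

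**Working it through.** **Cross-check of the text.**

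| Source | Baseline scar assessment? | Must the scar be new? |
|---|---|---|
| Protocol 7.1.1 | Assumed | – |
| Protocol 7.2.6, Table 1, 6.2.2 | Not scheduled; first at Week 4 | – |
| Protocol 3.3 (endpoint) | – | Yes, by its wording |
| SAP 10.1 (derivation) | Not used | No; presence only |
| SAP section 4 (adverse event) | Not used | Yes, but no scheduled record to show it |

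So 7.1.1 conflicts with three other places in the protocol, and the SAP derivation is looser than the endpoint it implements.

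**What the lesion map can and cannot do.** Sites are mapped from Baseline through Week 12, and the map is meant to help with scar assessment (4.1, 7.1.1). It lets an evaluator question a scar at a place where no lesion was mapped. Three gaps remain:

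- Only active lesions are counted, and nothing tells staff to mark existing scars.
- Treatment extends about 1 cm around each lesion (1.2.1, 8.5) and scars are sought in treated areas, so an old scar beside a current lesion falls inside the search area.
- A lesion that appears and clears between visits is never mapped, so an unmapped scar is not proven old.

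The requirement in 7.2.6 that a scar come from a molluscum lesion does not close the gap, because a scar from an earlier lesion also meets it.

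**Size.** The documents give no scar rate and no prevalence of scars at entry, so there is no plan figure to reproduce and every input here is an assumption. Let b be the share of subjects with an old scar that ends up counted, equal in both arms, and q the true new-scar rate, independent of b.

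Reported rate = b + (1 − b)q. Reported difference = (1 − b)(q_active − q_vehicle).

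Example, b = 5%: vehicle 0.05 + 0.95 × 0.02 = 0.069; active 0.05 + 0.95 × 0.04 = 0.088; ratio 0.088/0.069 = 1.28; difference 0.95 × 2.0 = 1.9 points.

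| b | Vehicle (true 2%) | Active (true 4%) | Ratio | Difference (points) |
|---|---|---|---|---|
| 0% | 2.0% | 4.0% | 2.00 | 2.0 |
| 5% | 6.9% | 8.8% | 1.28 | 1.9 |
| 10% | 11.8% | 13.6% | 1.15 | 1.8 |
| 20% | 21.6% | 23.2% | 1.07 | 1.6 |

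With true rates of 5% and 2%, the ratio goes from 2.50 to 1.41, 1.23 and 1.11 over the same values of b, and the difference from 3.0 to 2.85, 2.7 and 2.4 points. The pattern is the same: absolute rates rise in both arms, the ratio moves toward 1, and the difference changes little.

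**The case against.** A reader might infer that old scars cannot be told from new ones and will be counted as on-study scars. The documents do not support that. Besides the map, the endpoint applies only after clearance, 7.2.6 requires molluscum origin, the SAP limits the adverse event to a new scar, and causality assessment (9.3) asks about timing and alternative causes. The Baseline physical examination may also pick up some scars, although it does not name them. What sites were told in lesion-count training is not visible in these documents. These safeguards make the separation unreliable in some positions on the skin; they do not make it impossible.

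A reader might also infer a large number of false adverse events. Section 4.1 says small pits heal over time, and pits below 5 mm in diameter and 1 mm in depth are not adverse events under 7.2.6. Small pits of that kind would not qualify under the protocol. This does not protect the SAP endpoint, whose second question has no size limit.

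Finally, a reader might infer that a real treatment difference would be hidden. That is mostly an effect on the ratio. The trial is randomized and blinded, so old scars should be roughly balanced between arms, and SAP 11.3 plans only descriptive summaries of scarring, with no ratio and no test. All of this stands, and it limits the point to a modest one.

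**Conclusion.** The point holds in a limited form. Section 7.1.1 conflicts with Table 1, 6.2.2 and 7.2.6, and nothing in the SAP 10.1 derivation excludes a pre-existing scar. Scars at or near a mapped lesion may not be reliably separated from new ones.

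The consequence is confined to the exploratory, descriptive scar and keloid endpoints and to scar adverse event reporting. The primary and secondary efficacy analyses are unaffected. Absolute scar rates may be inflated in both arms and their ratio pulled toward 1, with little change in the risk difference. The size is unknown: the 5% to 20% range is illustrative, and the bias is zero if evaluators screen out every old scar. The change is worth making because it is cheap and the misclassification is foreseeable.

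**What to change.** 1. Reconcile 7.1.1 with Table 1, 6.2.2 and 7.2.6 by adding the existing Scarring/Keloid form at Baseline and marking existing scars on the lesion map already drawn at that visit.
2. In SAP 10.1, count a subject as developing a scar or keloid only if it was not recorded at Baseline, meaning not marked at that site on the map. Apply the same test to adverse events for new scars.
3. Do not add a rule based on enlargement of an old scar. The eCRF questions quoted in SAP 10.1 are yes/no and record neither size nor site, so growth could not be derived without new measurements.
4. If Baseline data cannot be added, correct 7.1.1 and label the endpoint scar presence, not scar development.

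The cost is a few minutes per Baseline visit, at which the skin is already mapped and a physical examination done, plus a small protocol and eCRF change and one clause in the SAP.

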7.3 Protocol Deviations

This study will be conducted as described in this protocol, except for in emergency situations in which the protection, safety, and well-being of the subject requires immediate intervention, based on the judgment of the investigator (or a responsible, appropriately trained professional designated by the investigator). In the event of a significant deviation from the protocol due to an emergency, accident, or mistake, the investigator or designee must contact the CRO at the earliest possible time by telephone. This will allow an early joint decision regarding the subject's continuation in the study. This decision will be documented by the investigator and the CRO.

